11.4 Analysis

11.4.1 For the Primary Objectives, all analyses point and (1-sided Wilson type 90% lower) CI estimates of the primary endpoint (PSA50) will be calculated.

Adverse events will be tabulated by incidence and severity graded according to the National Cancer Institute – Common Terminology Criteria for Adverse Events (CTCAE) version 4.03. Other statistics will include point and (2-sided) CI estimates of overall toxicity and of specific types of toxicity.

11.4.2 For Secondary Objective 1, descriptive statistics of TTPR will be used to summarize the time to PSA response. These descriptives will include N, median, mean, standard deviation (SD), interquartile range (IQR), minimum, and maximum.

11.4.3 For Secondary Objectives 2 and 3, the censored distributions of duration of response (RD) and PSA progression free survival (PFS) will be summarized with the Kaplan-Meier (K-M) survivorship estimate. A graph of the K-M curve for PRD and for PPFS will be generated along with the Hall-Wellner 90% confidence band, and a display of the number of patients at risk at several time points, below the X-axis. Summary statistics (6-month rate, 12-month rate, median, etc.) will be calculated from the K-M life table, each one with its respective 80% confidence interval (CI).

11.4.4 For the Correlative (Exploratory) Objectives, frequency distributions of all categorical variables (grade of specific types of toxicity, and categorical biomarkers or other correlatives) will be generated. Serial PSA levels will be displayed using spaghetti plots, and changes in PSA using waterfall plots.

Descriptive statistics will be used to summarize all continuous correlatives (e.g., PSA, continuous biomarkers and other correlatives), and changes in them pre/post ESK981 treatment. Gene expression levels will be \log_2 transformed prior to descriptive analysis. Multiple boxplots and scatterplots will be used to display summary statistics of biomarkers/correlatives and interrelationships between continuous correlatives, respectively.

Details of the planned determination of bioinformatics correlatives are given in Section 9. Response (whether PSA50 or overall), a categorical clinical outcome, will be statistically modeled as a function of each correlative using exact logistic regression. TTPR, a continuous

uncensored clinical outcome (limited to only the PSA50 responders), will be statistically modeled as a function of each correlative using linear regression.

Time to event clinical outcomes (PRD and PPFS) will be statistically modeled as a function of each correlative using Cox proportional hazards regression. Examples of categorical correlatives include: gene mutation status (Sec. 9.1 and 9.2); AR dependence (Sec. 9.3); and vacuolization status or vascularization status (Sec. 9.6). Examples of continuous correlatives include: kinase expression levels (Sec. 9.4); CTC and DTC counts (Sec. 9.5); and levels of Ki67, AR, and LC3 (Sec. 9.6).

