9.3 The association of AR signaling with Exceptional Response to ESK981

Furthermore, since modulation of androgen receptor (AR) signaling through tyrosine kinases is observed as a mechanism of resistance to androgen deprivation therapy and androgen-independence, we hypothesize that the loss of dependence on AR signaling will be an additional independent predictor of response and outcomes. The trial is designed to enrich for AR-independent patients in the Enza/Abi-refractory cohort who will allow us to evaluate our hypotheses. Aggregate scores of AR-dependence and AR-independence will be derived from the expression levels of canonical AR targets and trans-differentiation markers.

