11.3 Design

11.3.1 We will utilize a single group single-stage Phase II design for the study. Patients will receive 160mg (4 capsules) of ESK981 dosed once daily for five consecutive days followed by a two consecutive day treatment break, for a cycle of 28 days. After 8 weeks (2 cycles) of ESK981, patients will be evaluated for their rate of PSA decline of $\geq 50\%$ from baseline (PSA50), using the PCWG3 criteria. Extrapolating from the data summarized on PSA50 response at any time by Cheng et al,¹⁶ we hypothesize that the 8-week PSA50 rate in patients similar to patients eligible for this protocol is approximately 20%. We also hypothesize that the 8-week PSA50 rate for ESK981 treated patients will be approximately 30%.

11.3.2 We seek preliminary evidence that the true 8-week PSA50 rate for patients on ESK981 exceeds the hypothesized reference value of 20%. Having a directional hypothesis, the PSA50 rate will be estimated with a 1-sided Wilson type 90% lower confidence interval (CI). With precision defined as a CI half-width (distance from the PSA50 estimate to the lower 90% confidence limit (CL)) of 0.100, a sample size of N=27 patients and a sample estimate of PSA50 = 30% would have a lower CL = 0.201. This would indicate that the true 8-week PSA50 rate was $> 20\%$, with 90% confidence.

11.3.3 The required sample size of N=27 was determined from the "Confidence Intervals for One Proportion" program within the PASS 15 software.¹⁷

11.3.4 Sample size adjustment for non-compliance will be made as follows. A major goal of this study is to evaluate the efficacy (in addition to the effectiveness) of ESK981 upon the PSA50 rate, safety, and tolerability. For each individual patient, we will allow for an ESK981 treatment non-compliance of up to 25% (i.e., up to 25% of pills were not taken).

Our initial analytic focus will be on the patients who are eligible (per Section 3), and evaluable (i.e., were on treatment for at least Cycle 1 [28 days]), and compliant (took at least 75% of the intended ESK981 pills during Cycle 1).

The patients meeting all 3 such requirements will be considered the eligible, evaluable, and compliant ("EEC") subset. We anticipate that up to 15% of the enrolled patients will not become EEC for one reason or another.

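### The correlative models use PSA change only as PSA50 yes/no and list the AR-dependence score as categorical without a cut-point; modelling both as continuous would recover power at no extra data cost

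*Combined protocol and SAP*

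**What the plan says.** **Outcome.** Section 11.4.4: "Response (whether PSA50 or overall), a categorical clinical outcome, will be statistically modeled as a function of each correlative using exact logistic regression". The same section displays serial PSA in spaghetti plots and PSA change in waterfall plots, and summarises continuous measures, PSA among them, descriptively. No model takes PSA change as its outcome.

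**Other outcome models.** Time to PSA response is modelled by linear regression in PSA50 responders only. Duration of PSA response and PSA progression-free survival (PPFS) are modelled by Cox regression. Under 11.2.2 the duration clock starts at PSA50, so that endpoint also exists only in responders.

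**AR score.** Section 9.3: "Aggregate scores of AR-dependence and AR-independence will be derived from the expression levels of canonical AR targets and trans-differentiation markers". Section 11.4.4: "Examples of categorical correlatives include: gene mutation status (Sec. 9.1 and 9.2); AR dependence (Sec. 9.3". Neither place gives a cut-point. Kinase expression, CTC and DTC counts, and Ki67, AR and LC3 levels are listed as continuous.

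**Data available.** Section 8.2.1 schedules PSA on days 8, 15 and 22 of Cycle 1 and on day 1 of every later cycle. It calls for each man's percent change at 8 weeks, or earlier if he stops treatment.

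**Status.** Section 9 labels these analyses tertiary or exploratory. No alpha, effect size or power is stated for them.

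**The concern.** A man whose PSA falls by 51% and one whose PSA falls by 95% count the same in the response model. So do a man with a 49% fall and one whose PSA doubles. In 27 men with about 8 responders, that discards much of what was measured. The AR score is treated less favourably than the other expression markers, without a reason given, although Section 9.3 says the trial was designed to enrich for AR-independent patients so that this hypothesis could be evaluated.

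The biopsies at baseline and week 8 are mandatory (3.1.12), as are the repeated blood samples (3.1.13). At stake is how much those samples can show, and whether a null result from a weak analysis is read as evidence against a marker. No primary or secondary conclusion is affected.

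**Working it through.** **1. The plan's own figure.** Section 11.3.2 states that "a sample size of N=27 patients and a sample estimate of PSA50 = 30% would have a lower CL = 0.201". The Wilson lower limit with z = 1.2816 is [p + z²/2n − z·√(p(1−p)/n + z²/4n²)] / (1 + z²/n). With p = 0.30 and n = 27 it is 0.2011, so the figure reproduces. It concerns estimation of the PSA50 rate and says nothing about the biomarker models.

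**2. Inputs.** From the plan: n = 27 evaluable men, a 30% PSA50 rate (about 0.30 × 27 = 8 responders) and a 20% reference rate. Assumed, because the plan gives none: a bivariate normal marker and log PSA change, correlation 0.3 to 0.6, two-sided 5%, and a median split of the AR score.

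**3. Information kept.** Cutting a normal outcome so that a proportion p responds keeps φ(z_p)² / [p(1−p)], where φ is the normal density at the cut. A median split of the predictor multiplies this by 2/π = 0.637.

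| PSA50 rate | Outcome cut only | Effective n | Both cut | Effective n |
|---|---|---|---|---|
| 30% | 58% | 15.5 | 37% | 9.9 |
| 20% | 49% | 13.2 | 31% | 8.4 |

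**4. Simulated power** (n = 27, 30% PSA50 rate, 4,000 trials per row). The tests are Pearson with both variables continuous; an exact conditional test of PSA50 on the continuous marker, as in exact logistic regression; and Fisher's exact test with both cut. Percentages in brackets are relative losses against Pearson.

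| Correlation | Both continuous | PSA50 cut, marker continuous | Both cut |
|---|---|---|---|
| 0.3 | 34% | 21% (38%) | 12% (65%) |
| 0.4 | 57% | 34% (40%) | 20% (65%) |
| 0.5 | 78% | 51% (35%) | 30% (61%) |
| 0.6 | 93% | 71% (24%) | 46% (50%) |

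The last column depends on which half the median man joins, since 27 is odd. The table places him in the low half. Placed in the high half, power at correlations 0.4 and 0.5 is about 17% and 27%, losses of about 69% and 65%. Hence the range of 50–70%.

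**5. Sensitivity.**
- At a 20% PSA50 rate the loss is 36–49% with the outcome cut (33–46% against a Spearman test) and 61–71% with both cut. It is higher still if the median man joins the high half.
- At two-sided 10% and a 30% rate the losses are 16–33% and 43–63%.
- At correlation 0.7 they shrink to 15–22% and 36–46% across the two rates.
- A binary mutation with 30% prevalence and a 1 SD effect has 38% power on PSA50 against 60% on log PSA change, a relative loss of 1 − 38/60 = 37%. Only the outcome cut applies there.

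**6. Do the other models fill the gap?** Time to and duration of PSA response rest on about 8 men. Linear regression at n = 8 has power of about 16% at correlation 0.4 and 25% at 0.5. PPFS uses every man's PSA and does not depend on the 50% threshold, but it measures time to a PSA rise, not depth of decline.

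**The case against.** The case for leaving the plan alone has real substance.

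- **The analyses are exploratory.** They carry no power claim, and PSA50 is the primary endpoint, so modelling it is natural. Section 8.2 itself cautions against relying on PSA change. This limits the weight of the point but does not favour the coarser version of the same PSA data.
- **Most markers are not cut.** A reader might infer that the biomarker models in general lose half to two-thirds of their power. The documents do not support that: the listed kinase, cell-count and protein markers stay continuous, and mutation status is naturally binary. At the planned 30% rate a loss of that size arises only for a split AR score.
- **Exact logistic regression adds no visible penalty for continuous markers.** An effective n of 15.5 at correlation 0.5 gives about 49% power by Fisher's z, and the simulation gives 51%. A reader might blame the exact method; the loss comes from the cut.
- **A data-chosen AR cut is inference.** The plan lists examples, and men could be classed by the larger of the two AR scores with no tuned threshold. What stands is that no rule is written down.
- **A week-8 regression has its own weakness.** Under 11.3.4 the main analysis subset requires only 28 days on treatment, so some men may have no week-8 PSA. Dropping them could bias the result and erode the gain. This stands, and the fix must provide for it.
- **PPFS is a genuine partial remedy**, as are the planned descriptive plots. Neither models depth of decline.

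**Conclusion.** The point holds as a low-cost improvement to an exploratory analysis. No stated biomarker model uses continuous PSA change, and the AR score is listed as categorical with no rule for forming the categories.

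With 27 men, two-sided 5% and correlations of 0.3 to 0.6, the PSA50 cut costs roughly 25–40% of power for continuous markers at a 30% PSA50 rate and about 30–50% at 20%. If the AR score is also split at the median, the loss is about 50–70% at the 30% rate and more at 20%. These figures rest on assumed normality, correlations, alpha and cut-point; a looser alpha or stronger correlations reduce them. They also assume a usable PSA change in all 27 men.

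A reader might go further and infer that useful associations will usually be missed. That is too strong for continuous markers, where power on PSA50 is 51% at correlation 0.5 and 71% at 0.6. It is fair for a split AR score, where power stays below one half throughout the range.

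**What to change.** Amend 11.4.4 as follows.

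1. Add a model of log PSA change from baseline on each correlative. Use either a mixed model on serial log PSA, or linear regression on week-8 log(PSA/baseline) with the last on-treatment value for men who stop earlier, matching the provision in 8.2.1 for percent change. State which is used before the data are examined.
2. Enter the AR-dependence and AR-independence scores of 9.3 as continuous covariates. If categories are also wanted, write the rule down in advance.
3. Keep exact logistic regression on PSA50 and on overall response alongside; log PSA is no substitute for overall response.

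The cost is SAP wording, one more outcome per correlative and somewhat more exploratory output to interpret. No new patients, samples or assays are needed, and the primary endpoint, sample size and clinical conduct stay as they are.

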11.5 Expected Accrual Rate, Accrual Duration, and Total Study Duration

- 11.5.1 This will be a clinical trial involving Karmanos Cancer Institute (KCI) only. We expect to accrue 10-12 patients/year.
- 11.5.2 At that rate, we can accrue 32 patients (to obtain 27 EEC patients) in 32-38 months. Allowing an additional 4 months to finish determining all biomarkers and correlatives in all patients yields an estimated total study duration of 36-42 months.

12. REGULATORY AND PROTECTION OF HUMAN SUBJECTS

12.1 Roles and Responsibilities

12.1.1 Sponsor Investigator

The Sponsor Investigator is responsible for performing the following tasks:

- Responsibility for the overall conduct of the study and for monitoring the progress of the study
- Reviewing and ensuring reporting of Serious Adverse Events (SAEs)
- Reviewing data

12.2 Ethical Considerations

This study will be conducted in compliance with the protocol, GCP guidelines established by the International Conference on Harmonisation, and the ethical standards set forth in the Declaration of Helsinki 2004 (available at: www.laakariliitto.fi/e/ethics/helsinki.html).

12.3 Written Informed Consent

Before obtaining consent, members of the study team will review the rationale for the treatment program with the patient. The discussion will review the alternatives available (including hormonal therapy, chemotherapy, or supportive care as appropriate), the potential benefits of this program, the risks and the probability of their occurrence, and the procedures to minimize these risks. Should an adverse event occur, the provisions available to ensure medical intervention will also be reviewed. Why the risks are reasonable in relation to the anticipated benefits, incentives, or costs that will or may be incurred as a result of participating in the study, as well as the efforts to maintain confidentiality, will also be discussed with the patient.

Patients will be required to sign and date an informed consent form that meets the requirements of the Code of Federal Regulations (Federal Register Vol. 46, No. 17, January 27, 1981, part 50) and the IRB. The medical record will include a statement that written informed consent was obtained (and document the date that it was obtained) before the patient is enrolled in the study. The original signed document will become part of the patient's medical record, a copy will be forwarded to the lead site/sponsor pursuant to sponsor registration and to the PCCTC and a copy will be sent home with each patient.

The consent form will include the following:

- the nature and objectives, potential toxicities, and benefits of the intended study
- the length of therapy and likely follow-up required
- alternatives to the proposed therapy (including available standard and investigational therapies)
- the name of the investigator(s) responsible for the protocol
- the right of the patient to accept or refuse treatment and to withdraw from participation in this study
- Text regarding the consortium and the coordinating center should be added to all institutional informed consent documents and sections in the research authorization/HIPAA forms (e.g., "Prostate Cancer Clinical Trial Consortium")

12.4 Protection of Privacy

Patients will be informed of the extent to which their confidential health information generated from this study may be used for research purposes. After this discussion, they will be asked to sign a Notice of Privacy Practice research authorization/HIPAA form. The original signed documents will become part of the patient's medical records, and each patient will receive a copy of the signed documents. The use and disclosure of protected health information will be limited to the individuals described in the research authorization form. The research authorization form must be completed by the principal investigator and approved by the IRB.

12.5 Terminating or Modifying the Study

Adverse event and laboratory data from this trial will be assessed by the lead site or the sponsor's medical monitor on an ongoing basis. SAEs will be reviewed as they are reported to the lead site/sponsor, and the medical monitor will make an assessment regarding the safety of continuing or modifying the study. This assessment will be shared with the investigators either in writing or as part of a teleconference. Should the assessment of either the lead site/sponsor or the principal investigator be that the study should be terminated; the study will be closed to further accrual. Patients who are receiving an investigational agent will be assessed individually by the investigator to see if it is in the patients' best interest to continue, which might be the case for a patient that is responding to the intervention. Follow-up safety assessments will be performed for all patients who are terminated from the study prematurely.

APPENDIX A: PERFORMANCE STATUS CRITERIA

ECOG Performance Status Scale		Karnofsky Performance Scale	
Grade	Description	%	Description
0	Normal activity. Fully active, able to continue all predisease performance without restriction.	100	Normal, no complaints, no evidence of disease
		90	Able to carry on normal activity, minor signs or symptoms of disease
1	Symptoms, but ambulatory. Restricted in physically strenuous activity but ambulatory and able to carry out work of a light or sedentary nature (eg, light housework, office work).	80	Normal activity with effort, some signs or symptoms of disease
		70	Cares for self, unable to carry on normal activity or to do active work
2	In bed <50% of the time. Ambulatory and capable of all self-care but unable to carry out any work activities. Up and about more than 50% of waking hours.	60	Requires occasional assistance but is able to care for most needs
		50	Requires considerable assistance and frequent medical care
3	In bed >50% of the time. Capable of only limited self-care, confined to bed or chair >50% of waking hours.	40	Disabled, requires special care and assistance
		30	Severely disabled, hospitalization indicated. Death not imminent.
4	100% bedridden. Completely disabled, cannot carry on any self-care, totally confined to bed or chair.	20	Very sick, hospitalization indicated. Death not imminent.
		10	Moribund, fatal processes progressing rapidly
5	Dead	0	Dead

APPENDIX B: MEDICATIONS WITH THE POTENTIAL FOR DRUG-DRUG INTERACTIONS

Please refer to Tables 3-2 and 3-3 of the FDA drug interactions labeling website for examples of clinical inhibitors and clinical inducers of P450, respectively.¹⁸

Potent Inhibitors of CYP1A2, CYP2C8, or CYP3A4

Potent inhibitors of the CYP1A2, 2C8, or 3A4 include, but are not limited to, the following:

CYP1A2

- Fluvoxamine
- Ciprofloxacin
- Mexiletine
- Propafenone
- Zileuton

CYP2C8

- Gemfibrozil

CYP3A4

- Ketoconazole
- Indinavir
- Ritonavir
- Itraconazole
- Clarithromycin
- Telithromycin
- Aprepitant
- Diltiazem
- Erythromycin
- Fluconazole
- Grapefruit juice
- Verapami

This list is not comprehensive as new information is continually being identified.

Potent Inducers of CYP1A2, CYP2C8, or CYP3A4

Potent inducers of the CYP1A2, 2C8, or 3A4 include, but are not limited to, the following:

CYP1A2

- Smoking

CYP2C8

- Rifampicin

CYP3A4

- Rifampicin
- Carbamazepine
- Griseofulvin

This list is not comprehensive as new information is continually being identified.

Substrates of CYP3A4/5 With a Narrow Therapeutic Range

Substrates of CYP3A4/5 with a narrow therapeutic range include, but are not limited to:

- Alfentanil
- Astemizole
- Cisapride
- Cyclosporine
- Diergotamine
- Ergotamine
- Fentanyl
- Pimozide
- Quindine
- Sirolimus
- Tacrolimus
- Terfenadine

This list is not comprehensive as new information is continually being identified.

APPENDIX C: STUDY CALENDAR

	Screening	Treatment/Intervention Period					End of Tx (30 Days from last dose)	Follow-up Q 3 mos
		Cycle 1				Cycle 2 + beyond		
		Day -28 to Day -1	Day 1 (± 3 d)	Day 8 (± 3 d)	Day 15 (± 3 d)	Day 22 (± 3 d)	Day 1 (± 3 d)	
Informed consent and research authorization/ HIPAA form	X ^a							
Demographics, medical history, histologic and radiologic confirmation of disease	X							
Physical examination, vitals, weight, blood pressure	X	X	X	X	X	X	X	
EKG	X							
Height	X							
Performance status	X	X	X	X	X	X	X	
Concomitant meds	X	X	X	X	X	X	X	
Toxicity assessment	X	X	X	X	X	X	X	
Tumor measurements ^b	X	Tumor measurements will be repeated every 8 weeks (+/- 10 d)						
Laboratory tests ^c	X		X	X	X	X	X	
Correlative samples	X					X ^d	X	
Tumor Biopsies	X					X ^e		
Follow-up								X ^f

- a. May be obtained up to 60 days prior to initiation of study treatment.
- b. Radiographic evaluations will include a CT or MRI abd/pel and a bone scan or PET. Chest x-ray should be done if necessary for tumor assessment. Radiologic documentation will be provided for patients removed from study for progressive disease.
- c. Complete blood count, comprehensive chemistry panel including renal function (BUN, creatinine) and liver function tests (AST, ALT, total bilirubin), PSA, testosterone (at baseline).
- d. Whole blood samples will be collected every 4 weeks from screening to end of treatment (see lab manual).
- e. Tumor biopsies performed at the Cycle 3 visit (week 8, +/- 10 d) (see lab manual).
- f. Patients will be followed every three months for 5 years from end of treatment for survival and subsequent treatment.

